7.2 Statistical Analysis

Analyses will primarily be exploratory.

To assess the accuracy of low blood glucose values obtained with the sensor, time periods of sensor values below 60 mg/dl will be identified and sensor values will be compared with gold standard values obtained during the same time period.

- To assess overall accuracy, analyses will be conducted similar to those planned for the diabetic subject protocol. For analysis, the gold standard blood glucose values will be paired with the appropriate corresponding sensor values, and the difference between values will be computed. Accuracy will be evaluated by computing the mean and standard deviation for the following parameters and then constructing 95% confidence intervals around the mean: difference, absolute difference, relative difference and absolute relative difference.

Each accuracy measure will be computed on a subject level and then the mean, standard deviation, and 95% confidence interval around the mean will be computed across subjects.

The sensor failure rate will be determined. The frequency of missed sensor readings and the reasons will be tabulated. Adverse events will be tabulated and their incidence estimated.

After the first 10 subjects, the data will be assessed to determine whether any subjects have experienced periods of nocturnal hypoglycemia with the sensors and, if yes, whether the low values were corroborated on the gold standard measurements. If false low glucose values with the sensor occur, then consideration will be given to modifications in the protocol or data collection to try to determine why this is occurring.

References

1. Tamada, J.A., et al., Noninvasive glucose monitoring: comprehensive clinical results. *JAMA*, 1999. 282(19): p. 1839-44.
2. Pitzer, K.R., et al., Detection of hypoglycemia with the GlucoWatch Biographer. *Diabetes Care*, 2001. 24(5): p. 881-5.
3. Tierney, M.J., et al., The GlucoWatch Biographer: a frequent, automatic and noninvasive glucose monitor. *Ann Med*, 2000. 32: p. 632-41.
4. Garg, S.K., et al., Correlation of fingerstick blood glucose measurements with GlucoWatch Biographer glucose results in young subjects with type 1 diabetes. *Diabetes Care*, 1999. 22(10): p. 1708-14.
5. Eastman, R.C., et al., Use of the GlucoWatch Biographer in children and adolescents with diabetes. *Diabetes Care*, 2001. submitted for publication.

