1.2 Synopsis of Study Design

At five clinical centers, a pilot study will be conducted on 20 healthy subjects (7 to <18 years old) who do not have type 1 or type 2 diabetes nor history of the disease in the immediate family. Each subject will be hospitalized for approximately 26 hours to assess the accuracy of the continuous glucose monitors compared with 'gold standard' blood glucose measurements. The data will be evaluated after the first 10 subjects to determine whether any modifications in the protocol should be considered for the second 10 subjects.

During the hospitalization, each subject will simultaneously use both the GW biographer and CGMS sensors and have blood drawn for gold-standard blood glucose measurements every 60 minutes during the day and every 30 minutes overnight.

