1.3 Background Information on the GlucoWatch Biographer

The GlucoWatch biographer was developed and is distributed by Cygnus, Inc. It looks like a watch and is worn on the forearm, three or more inches from the wrist or elbow joint.¹ An adhesive pad incorporating two hydrogel discs attaches the device to the skin. Each disc is the size of a dime. A triple 'A' battery from the biographer sends a small current through the discs to pull glucose from

the interstitial fluid underneath the skin. The glucose in the interstitial fluid is then measured. The maximal current used is very small (that of the triple 'A' battery). Each cycle lasts for 20 minutes.

The biographer model to be used in the study (GlucoWatch 2 biographer) gives up to 6 readings per hour, for 13 hours. The subjects can read glucose values displayed on the biographer. It also has a high and low glucose alarm that can be set by the user for certain glucose levels of their choice (e.g., less than 70 mg/dl and/or more than 300 mg/dl). A two-hour warm-up time followed by a single glucose meter value is needed to calibrate the device. The GlucoWatch 2 biographer is the identical mechanical device as the GlucoWatch biographer, but the software has been changed to allow for a 2-hour instead of a 3-hour warm up, and readings are made every 10 minutes instead of every 20 minutes. This device will not require an IDE. The biographer can be affected by the following:

- Sweat. There are two small metal bars on the bottom side of the GlucoWatch biographer that measure how much sweat is on the skin. If excessive sweating is detected, the cycle will be skipped (i.e. no value given for that 10-minute period).
- Temperature. If the temperature or rate of change in temperature is beyond a pre-programmed level, the cycle will be skipped.
- Glucose values outside the range of 40-400 mg/dl are just read as either LOW or HIGH.

Subjects wearing the GlucoWatch biographer may develop erythema and a localized skin reaction to the adhesive used to secure the GlucoWatch biographer to the skin, or to the hydrogel iontophoresis pads. Very rarely a severe skin reaction could result in scarring.

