1.4 Background Information on the Continuous Glucose Monitoring System

The CGMS was developed and is distributed by Medtronic Minimed, Inc.⁷ This sensor uses a glucose oxidase based electrochemical sensor which generates 2 electrons for each glucose molecule oxidized. The current generated from measuring glucose is called the ISIG (Input SIGnal). The CGMS system is designed to measure blood glucose levels in a range of 40-400 mg/dl. The sensor is inserted subcutaneously and measures interstitial glucose. Lag times between changes in the serum glucose and changes in sensor output are generally between 4 and 9 minutes in animal studies.⁸ In human studies the interstitial glucose levels generally lag behind the blood glucose by 3 to 13 minutes.^{9,10} When functioning properly, the CGMS acquires glucose values every 10 seconds and these values are averaged in the monitor to provide a reading every 5 minutes (or 288 readings a day). Each sensor is designed to measure readings for 24 to 72 hours; many sensors will not function for a full 72 hours. The sensor can be inserted with equal success by patients and health care professionals, has been able to work in a broad age range (from 2 weeks to 74 years old), and sex, race and duration of diabetes do not appear to influence sensor function.^{11,12} The sensor is well tolerated with the only side effect being mild to moderate site irritation in 2% of patients.¹¹

The present version of the CGMS, which has been approved by the FDA, provides data in a retrospective analysis, much like a Holter monitor. The sensor does not display the glucose in "real

time” and does not have alarms to warn of hypoglycemia or hyperglycemia. The sensor requires at least 3 capillary glucose readings each day to validate sensor function and allow for development of a calibration equation. These calibration measurements are performed with a home glucose meter, and calibration is dependent upon the subject entering glucose values correctly into the sensor. The sensor cannot be worn in the water and must be kept dry. There are several reasons for sensor “failure”: 1) A faulty connection between the sensor and the connecting cable will cause frequent “disconnect” warnings. This problem can be avoided by careful insertion of the cable into the sensor, with the sensor and the cable connection maintained in a flat, horizontal plane at the time of connection. 2) The sensor becomes “fouled.”

CHAPTER 2

SUBJECT ELIGIBILITY AND ENROLLMENT

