3.3 Gold Standard Glucose Measurements

An intravenous catheter will be inserted in an arm vein. The area where the catheter will be inserted may be numbed with Elamax or EMLA cream for at least 15 minutes prior to catheter insertion.

The gold standard measurements will be timed to be on the hour and, when specified in the protocol to be performed overnight, on the half-hour. The first hourly measurement will be made at the first hour point that is at least one hour following insertion of the CGMS. Half-hourly measurements will be made from 9:00 p.m. to 7:00 a.m. If the catheter stops functioning, it will be replaced if there are any protocol-specified gold standard measurements still to be made.

The clinical centers either will use reinfusion of blood or will discard blood with each blood draw, depending on the standard practice at each center's CRC. The blood draws will be performed by the method in standard use at the CRC. The blood samples will be sent to a central lab.

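### Section 7.2 checks sensor lows only against same-period blood draws, ignoring the stated 3 to 13 minute lag, so real overnight CGMS lows of about 30 minutes can look false

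*Protocol*

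**What the plan says.** For low values, section 7.2 fixes the comparison: "time periods of sensor values below 60 mg/dl will be identified and sensor values will be compared with gold standard values obtained during the same" clock interval. It gives no offset, no tolerance and no outcome for a period without a draw. The looser wording about pairing with appropriate corresponding sensor values belongs to the overall-accuracy analysis, not to this rule.

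After the first 10 subjects, the same section asks about nocturnal lows and "whether the low values were corroborated on the gold standard measurements".

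Section 1.4, on the CGMS, states: "In human studies the interstitial glucose levels generally lag behind the blood glucose by 3 to 13 minutes". Section 1.2 sets the reference draws at "every 60 minutes during the day and every 30 minutes overnight", and section 3.3 fixes the night schedule: "Half-hourly measurements will be made from 9:00 p.m. to 7:00 a.m".

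**The concern.** If the sensor trails blood by some minutes, a true low in blood appears on the sensor shifted later by that amount. A draw in the last minutes of the sensor-low period then meets blood that has already recovered. A draw in the minutes just before the sensor-low period, when blood was low, lies outside the window. Under a delay, the same-period rule can therefore only push real lows towards looking false.

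With draws 30 to 60 minutes apart, a short low is judged on one draw, so one misplaced draw can decide it. Whether sensor lows are real is the open question of section 1.1. Section 7.1 justifies the 20 subjects by the chance to answer it, and the 10-subject look may lead to protocol changes on the same evidence. Section 1.1 also singles out 30 minutes: 18 of 31 children had at least that much time below 60 mg/dl in the first 24 hours, mainly overnight.

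**Working it through.** **Draw schedule.** Section 3.3.1 implies 24 hourly draws plus 10 half-hour draws overnight, 34 in all. Then 34 × 0.3 ml = 10.2 ml and 34 × 1.3 ml = 44.2 ml, as the protocol states. The spacing used below is therefore the protocol's own.

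**Inputs.** Lag L = 3 to 13 minutes (section 1.4), with 8 as the midpoint. Draw spacing I = 30 minutes from 9 p.m. to 7 a.m., otherwise 60 minutes (sections 1.2 and 3.3).

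**Assumptions.** The sensor is perfect apart from a pure delay. Blood is below 60 mg/dl from 0 to D minutes, so the sensor is low from L to L + D. The low starts at a random point relative to the draw times. A draw corroborates if it is below 60 mg/dl; the protocol sets no cut-off, so this is assumed.

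**Formulas.**
- No draw in the sensor-low period: max(0, 1 − D/I).
- For D ≤ I and L ≤ D, the period holds at most one draw. It falls after recovery with probability L/I, or L/D given that there is a draw.
- A draw that is both in the period and truly low is certain once D − L ≥ I.

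**The 30-minute low overnight.** One draw is certain (1 − 30/30 = 0). It falls after recovery in 3/30 = 10%, 8/30 = 27% or 13/30 = 43% of cases.

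**Other durations (L = 3 to 13).**

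| Low | Time | No draw | Given a draw, none is low |
|---|---|---|---|
| 15 min | night | 50% | 20% to 87% |
| 20 min | night | 33% | 15% to 65% |
| 30 min | night | 0% | 10% to 43% |
| 45 min | night | 0% | 0% |
| 120 min | night | 0% | 0% |
| 30 min | day | 50% | 10% to 43% |
| 45 min | day | 25% | 7% to 29% |
| 60 min | day | 0% | 5% to 22% |

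At 45 minutes overnight, even the longest stated lag leaves 45 − 13 = 32 minutes of overlap, more than the 30-minute spacing, so at least one draw is concordant. A 2-hour overnight low has four draws, of which at most one is discordant.

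**Does shifting the window help?** Shifting by the true lag takes the 30-minute overnight figure to 0%. Shifting by one assumed lag need not: for a 30-minute low the miss rate becomes |assumed − true|/30. With 10 minutes assumed and 3 true, that is 7/30 = 23%, against 10% unshifted. The shift does harm whenever the true lag is below 5 minutes.

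Using several shifts avoids this. Suppose the true lag lies between two of the shifts 0, 3, 8 and 13. The smaller shift fails only if a draw falls just after recovery. The larger fails only if a draw falls just before blood went low. Adjacent shifts differ by at most 5 minutes and draws are 30 minutes apart, so for a 30-minute overnight low both cannot happen. The chance of being uncorroborated at every shift is 0% for any lag from 0 to 13 minutes.

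**The case against.** The best defence is that section 7.2 sets no scoring rule. It compares values, calls the analyses primarily exploratory, and states no cut-off and no false-low proportion. A draw soon after recovery may be only slightly above 60 mg/dl, and a reader looking at values would see that. Lag handling could also be settled in a statistical analysis plan. This stands in part: real lows *can* look false, but it does not follow that they *will* be scored so. The protocol nevertheless states the window itself, and the question at the 10-subject look is framed as corroborated or not.

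A reader might infer three stronger points. The documents support none of them.

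- **The sample-size rationale fails.** Section 7.1 speaks of prolonged lows, and section 1.1 reports some of two hours or more. These are judged adequately overnight. Section 1.1 also does not say whether its 30 minutes were one unbroken run.
- **The biographer is hit harder, which distorts the device comparison.** No lag is given for it; the 3 to 13 minutes stand in the CGMS section. Section 1.3 says "Each cycle lasts for 20 minutes" but also gives readings every 10 minutes for the model used. Any added delay would be a guess.
- **Lows without a draw result from ignoring the lag.** They come from the draw spacing, and shifting the window leaves their frequency unchanged. Overnight they vanish from 30 minutes upward, and the 10-subject look concerns nocturnal lows.

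**Conclusion.** The point holds in a narrow form. The same-period window in section 7.2 does not allow for the lag stated in section 1.4, and the resulting error runs one way, towards calling real lows false. For a real CGMS low of 30 minutes overnight, the chance that its only draw misses the low is 10% to 43%. Shorter lows with a draw fare worse. At the stated lags, overnight lows of 45 minutes or more always keep a concordant draw; by day, lows of up to about an hour are affected.

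The figures rest on a pure delay, equal low durations in blood and sensor, random timing against the draws, and a yes/no reading at 60 mg/dl. Comparing values would soften them. No size is claimed for the biographer. Priority is minor to moderate.

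**What to change.** In section 7.2, and in the same form at the 10-subject look:

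1. Keep the same-period comparison. For each sensor-low period, add the comparison with the window moved back over the stated lag range, for example 0, 3, 8 and 13 minutes. Do not replace the rule by one assumed lag.
2. Call a low false only if it is uncorroborated across that whole range. Report a low whose answer changes with the shift as unresolved.
3. Label a period with no draw in the window as not assessable, and leave it out of any false-low proportion.
4. Report by duration: under 30, 30 to 60 and over 60 minutes.

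The cost is a change of wording and a little more analysis, with no new blood draws, visits or subjects. The downside is that some short lows will be reported as unresolved.
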